For example, to assess the effects of memantine on "gating" measures in schizophrenia patients, the primary measure will be evaluated by 2-way repeated-measure ANOVA of PPI with memantine dose and prepulse interval as within-subject factors. The hypothesis that memantine will increase PPI in schizophrenia patients will be confirmed by a significant effect of dose (active > PBO) or significant dose x interval (int) interaction and post-hoc comparisons at one or more prepulse intervals. Existing data (see above) provide a strong *a priori* prediction that the 120 ms prepulse interval will be most sensitive to PPI-enhancing effects of MEM. The effect size (d) for PPI-enhancement by 20 mg memantine in HCS was 0.91; with a similar "d" in patients, 30 patients/dose yields power of 0.92 to detect the predicted memantine effects; with maximum expected attrition (n=24), power is 0.85. Past findings also lead to the prediction that these MEM effects would be most robust in subjects exhibiting the lowest basal PPI levels (d=1.80). Using a median split of mean basal (screening) PPI levels, ANOVA as above will detect a significant interaction of memantine dose x basal PPI level, or dose x basal level x int, and significant post-hoc comparisons at one or more prepulse intervals (again, 120 ms being the strongest *a priori* candidate). Given the published "d" in control subjects, a comparable "d" in the proposed 12-15 "low PPI" patients/dose group would yield power >0.95 to detect the predicted memantine effects.

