Lastly, based on the impact of basal PPI level and personality measures in controls, we hypothesize that a critical moderating factor underlying PPI memantine sensitivity is COMT Val158Met genotype; specifically, we predict that “Val/Val” individuals will be most sensitive to memantine-enhanced PPI. This will be tested in two ways: first, by ANOVA as above, with COMT status as a between-subject factor, and memantine dose and prepulse interval as within-subject factors. Significant genotype x dose or genotype x dose x int interactions, with appropriate post-hoc comparisons, would confirm the hypothesis. Estimating $d=1.53$, based on the mean “d” of two “COMT phenotypes” in controls – low basal PPI ($d=1.80$) and high “novelty seeking” personality ($d=1.27$) - the proposed 11 Val/Val and 7 Met/Met patients/dose group would yield power of 0.90 to detect genotype-sensitive memantine effects. It is possible that various factors (including a skewed distribution of allele frequencies, or substantial genotype effects on basal PPI levels) might preclude detection of a significant 2- or 3-way interaction. A secondary (albeit weaker) test of the hypothesis will utilize separate ANOVAs in Val/Val vs. Met/Met subgroups, with predicted PPI-enhancing effects of memantine in the Val/Val but not Met/Met subgroups. Previous reports also predict a significant main effect of genotype, with PPI levels following the Met/Met>Val/Met>Val/Val gradient. Logistic regressions might be used, with genotype coded to reflect “dose” of the Met allele (Val/Val=0, Val/Met=1, and Met/Met=2), to assess the distribution of the neurophysiological and neurocognitive measures. All analyses will be conducted independently for each dose group. If comparable effects are evident with 10 and 20 mg doses, dose groups may be pooled to increase power for exploratory analyses (e.g. to detect genotype x drug effects).

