30. PROCEDURES FOR SURROGATE CONSENT AND/OR DECISIONAL CAPACITY ASSESSMENT

Schizophrenia patients who have been identified for participation in our studies will also be enrolled in IRB-approved clinical trials of cognitive training with [name]. [name] has approval to screen and administer surrogate identification process. Any patients that have been identified as having impairment in their decision-making ability will be determined by [name] and will not be referred to our studies.

Revision date: October 29, 2010

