Statistical Analysis Plan

Biomarker Strategies for Medication-Enhanced Cognitive Training in Schizophrenia

NCT01555697

NIMH-R34-MH093453-NS

Latest IRB approval date: August 17, 2019

IRB expiration date: August 15, 2020

The primary statistical considerations for these data are those required to test the primary hypothesis that memantine (MEM) would enhance sensorimotor gating and neurocognition in schizophrenia (SZ) patients. The operational measure of sensorimotor gating was prepulse inhibition of startle (PPI). The primary hypothesis was tested by a 2-way repeated-measure ANOVA of PPI with MEM dose and prepulse interval (10, 20, 30, 60 or 120 ms) as within-subject factors. The key dependent measure was %PPI, calculated according to common practices in the literature. The hypothesis that MEM will increase PPI in SZ patients was to be confirmed by a significant main effect of drug (active > PBO) or significant interaction among the variables of drug, dose (10 or 20 mg), diagnosis (healthy subject (HS) or SZ) or prepulse interval, and informative post-hoc comparisons. The assumptions behind these analyses range from the standard assumptions underlying the use of parametric analyses, to those specific to prepulse inhibition, e.g. related to the potential confounding effects of drug or diagnosis effects on startle magnitude. Data were demonstrated to be normally distributed and drug effects on PPI were shown to be independent of changes in startle magnitude. Analyses confirmed the hypothesis for the 20 mg dose of MEM in SZ patients.

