The same general analytic approach was applied towards MEM effects on neurocognition, assessed via the MATRICS Comprehensive Cognitive Battery (MCCB). Here, neurocognitive domain (7 domains) was a within-subject variable along with drug (active vs. PBO), and diagnosis and dose were between-subject factors. The dependent measure was MCCB T-score for each of the 7 domains, as well as a single comprehensive T-score. The hypothesis that MEM will increase MCCB scores in SZ patients was to be confirmed by a significant main effect of drug (active > PBO) or significant interaction among the variables of drug, dose (10 or 20 mg), diagnosis (healthy subject (HS) or SZ) or MCCB domain, and informative post-hoc comparisons. Again, the assumptions behind these analyses range from the standard assumptions underlying the use of parametric analyses, to those specific to neurocognitive performance, e.g. related to the potential confounding effects on levels of consciousness (i.e. increasing or decreasing alertness). Data were demonstrated to be normally distributed and drug effects on MCCB were shown to be independent of changes in self-assessed drowsiness. Analyses failed to confirm the hypothesis that MEM acutely enhanced neurocognition, in either HS or SZ patients.

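### The SAP text postdates the results and words a broader confirmation rule than the 2010 protocol, so whether the 20 mg PPI claim met the pre-specified test cannot be verified

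*SAP*

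**What the plan says.** **Protocol, section 9, item j (Statistics).** The PPI test in schizophrenia patients is a "2-way repeated-measure ANOVA of PPI with memantine dose and prepulse interval as within-subject factors". The criterion for the hypothesis reads: "will be confirmed by a significant effect of dose (active > PBO) or significant dose x interval (int) interaction and post-hoc comparisons". Any of the intervals may supply those comparisons. Earlier data support a "prediction that the 120 ms prepulse interval will be most sensitive to PPI-enhancing effects of MEM". On the two patient dose groups: "All analyses will be conducted independently for each dose group". Pooling them is allowed only for exploratory work, and only if the two doses look comparable. Working memory is tested by a one-way ANOVA with drug as the within-subject factor. Alpha is 0.05. The document closes with "Revision date: October 29, 2010".

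**SAP.** It first names the same two-way ANOVA and lists five intervals (10, 20, 30, 60 and 120 ms). It then says confirmation would come from a drug main effect, or from a significant interaction among drug, dose (10 or 20 mg), diagnosis or interval, together with post-hoc comparisons described only as informative. No alpha and no priority interval are given. The same paragraph reports that assumptions were met and that "Analyses confirmed the hypothesis for the 20 mg dose of MEM in SZ patients". For cognition, the model has the seven MCCB domains and drug within subject, dose and diagnosis between subjects, and a composite score as well. The result is again stated alongside the rule: "Analyses failed to confirm the hypothesis that MEM acutely enhanced neurocognition, in either HS or SZ patients". The only dates on the SAP are IRB dates (approval August 2019, expiry August 2020). No authoring, lock or unblinding date appears.

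**The concern.** A plan that reports its own results cannot serve as evidence that its rule came first. That would matter little if its rule were the protocol's, but it is wider. The documents do not show when the extra terms were adopted, and the SAP gives no qualifying effect, F, p or n for the PPI result.

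At stake is the status of the main positive finding. If the 20 mg result met the protocol's patient-only, single-dose-group test, it is a pre-specified result. If it came through a dose-group or diagnosis interaction, it rests on a rule with no documented pre-results existence. The SAP as written leaves both possibilities open.

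**Working it through.** **1. The two rules side by side**

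| Feature | Protocol 9.j | SAP |
|---|---|---|
| Population for the PPI test | patients | patients and healthy subjects enter through a diagnosis factor |
| Dose groups | analysed separately; pooling exploratory | dose is a factor in the rule |
| Qualifying effects | drug; drug x interval | drug; any interaction among drug, dose, diagnosis, interval |
| Priority interval | 120 ms | none stated |
| Post-hoc step | Tukey, at one or more intervals | informative, undefined |
| Cognition | one-way ANOVA of working memory | seven-domain model plus composite |

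**2. Internal mismatch in the SAP.** The two-way model it names has drug and interval as its only factors, so it has one interaction: drug x interval. It cannot yield a diagnosis or dose-group interaction. Dose group is between subjects by design (30 patients at 10 mg, 30 others at 20 mg) and is called so in the SAP's own MCCB paragraph. The listed interactions need a larger model that the PPI paragraph does not specify.

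**3. The plan's own figure.** The documents give no false-positive rate. The number attached to the PPI test is power: 0.92 at n = 30 and 0.85 at n = 24, with d = 0.91. A two-sided 0.05 two-sample t-test gives 0.934 and 0.870, within two points of each. This does not bear on the timing question.

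**4. Nominal routes with no drug effect.** Count a main effect only when active exceeds placebo (probability 0.025 at two-sided 0.05; the protocol does not state sidedness) and an interaction at 0.05, treating effects as independent.
- Protocol rule, 20 mg patients: 1 - 0.975 x 0.95 = 0.074.
- Protocol rule, either dose: 1 - (1 - 0.074)^2 = 0.14.
- SAP rule, drug main effect plus the 7 interactions that contain drug: 1 - 0.975 x 0.95^7 = 0.32.

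**5. Simulation with no drug effect and no post-hoc step.** 30 per group (patients 10 mg, patients 20 mg, healthy 20 mg), five intervals, correlation of the drug-placebo difference between intervals 0.3 or 0.6, 20,000 trials each.

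| Route | Rate |
|---|---|
| Protocol rule, 20 mg patients | 0.072 |
| Protocol rule, either dose | 0.14 |
| Patients pooled, dose as factor | 0.16 |
| Three groups, dose and diagnosis contrasts | 0.23 |
| Any of these | 0.30 |

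A separate simulation with four crossed groups gave 0.073 and 0.138 for the protocol rule, and 0.313 for the eight drug-containing effects. That layout assumes a healthy 10 mg group, which the protocol does not plan.

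**6. The rate for the claim actually made.** The SAP claims an increase, in patients, at 20 mg. So require that any significant route be backed by a positive active-over-placebo result in the 20 mg patients.
- No effect anywhere: about 0.03 with Bonferroni-adjusted intervals, and 0.06-0.08 unadjusted.
- Healthy subjects respond (assumed shift 0.7 SD), patients do not: about 0.04 to 0.11, depending on adjustment and correlation.

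**The case against.** The strongest reply is that the SAP names the protocol's two-way ANOVA as the test of the primary hypothesis, almost unchanged, before it reaches the broader sentence. The result is claimed for one dose in patients, which fits the protocol's instruction to analyse each dose group separately. The natural reading is that the 20 mg claim came from the protocol test. This stands as a plausible reading. It does not settle the matter, because no effect or p-value is reported and the sentence defining confirmation lists effects outside that test.

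A reader might infer that the broader rule was fixed once the outcome was known. The documents do not support that. The SAP phrases the rule as an earlier intention, while assumptions and results are in the simple past, so a version between October 2010 and the results may exist. A rule of the same form was applied to cognition and reported as failed, which counts against tailoring, though it does not date the rule.

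A reader might also take 30% as the false-positive rate of the 20 mg claim. It is not: it counts hits at 10 mg only and interactions in either direction, and it skips the post-hoc step that the SAP requires. The seven-domain model concerns cognition and cannot inflate the PPI claim. Finally, the protocol's own either/or rule exceeds 0.05 before post-hocs, so the SAP is not the only source of the excess.

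**Conclusion.** The concern holds in a limited form. The SAP text postdates the results, its rule is broader than the only rule in the documents that predates them, and it does not identify the effect behind the 20 mg confirmation. The pre-specified status of that claim is unverified. To say that it cannot be a pre-specified test would go too far, since it may have met the protocol rule.

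The possible inflation for the 20 mg claim itself is modest: about 3-8% with a positive 20 mg patient post-hoc required, against about 7% for the protocol rule without one, and up to about 11% if only healthy subjects respond. The figure of about 30% bounds any claim by any route. These sizes assume 30 per group, equal correlations between intervals, the listed set of models and a post-hoc filter that the SAP leaves undefined. The 0.7 SD healthy-subject shift is also an assumption. The textual finding needs none of these.

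**What to change.** - State in the SAP that its text postdates the analysis, and give the date on which the dose-group and diagnosis terms were added.
- Report the protocol's two-way test in the 20 mg and 10 mg patient groups separately: which effect, degrees of freedom, p, n, and the 120 ms comparison. Report the protocol's one-way working-memory test as well.
- Keep the word confirmed for 20 mg only if that protocol test meets it.
- Label the SAP analyses outside protocol 9.j as post hoc unless a dated pre-results version can be produced. These are the dose-group and diagnosis interactions, the seven-domain MCCB model and the composite. The genotype test in 9.j keeps the status the protocol gives it.

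The cost is rewording, relabelling and reporting tests on existing data; no new data are needed. The downside is that the headline PPI claim may become exploratory. If the protocol test was met, the claim becomes firmer than the present text makes it.

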1. The "WITHIN-SUBJECT" study involves a single drug. There will be 2 test days – on the additional test day, subjects will receive either placebo or an active dose of one of the following: amphetamine (20 mg), memantine (10 mg) and memantine (20 mg). Some studies may require a venopuncture for genetic analysis as discussed above. A "model" example of a WITHIN-SUBJECT test schedule is shown below:

Test Day 1

0815-0845 Subject signs required forms, provides urine sample, eats standardized breakfast, venopuncture (if required)

0845-0900 Vital signs (VS) check, hearing and vision test, symptom rating scale.

0900-0915 drug or placebo administration.

0915-0930 VS check; symptom rating scales.

0930-0945 EMG electrodes applied.

0945-1000 VS check; symptom rating scales.

1000-1125 Startle response measurement, including PPI, habituation and intensity assessment.
1125-1140 VS check; symptom rating scales.
1140-1155 Visual LI or Visuospatial priming or MCCB
1155-1210 VS check; symptom rating scales.
1210-1300 Subject offered lunch from cafeteria.
1300-1600 VS check hourly; subject dismissed if VS within established parameters at 1600.

Test Day 2: 7-30 days after Test Day 1

0815-0845 Subject signs required forms, provides urine sample, eats standardized breakfast, venopuncture (if required)
0845-0900 Vital signs (VS) check, hearing and vision test, symptom rating scale.

0900-0915 drug mg or placebo administration: WHICHEVER DOSE WAS NOT RECEIVED ON TEST DAY 1

0915-0930 VS check; symptom rating scales.
0930-0945 EMG electrodes applied.
0945-1000 VS check; symptom rating scales.
1000-1125 Startle response measurement, including PPI, habituation and intensity assessment.
1125-1140 VS check; symptom rating scales.
1140-1155 Visual LI or Visuospatial priming or MCCB
1155-1210 VS check; symptom rating scales.
1210-1300 Subject offered lunch from cafeteria.
1300-1600 VS check hourly; subject dismissed if VS within established parameters at 1600.

Subjects will be instructed to not eat on the morning of the test, and instead will be served a standardized meal 30 min prior to drug administration, so as to maintain a controlled and consistent impact on drug absorption.

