j. Statistics: Tests for homogeneity of variance are performed, and if appropriate, analyses of variance (ANOVA) used. Statview/Superanova software is used on the Macintosh. For startle data, P-Alone amplitude, PPI and startle latency are analyzed by ANOVAs; for drug studies, drug dose is used as a within-subject factor. Habituation is detected by a significant effect of trial block. Visuospatial priming is analyzed separately for baseline, facilitation, and inhibition conditions using ANOVAs. Baseline is a measure of visuospatial response time, while facilitation and inhibition scores are measures of sensorimotor modulation. Nonparametric statistics are used for the Latent Inhibition analyses because data from this test tend toward a bimodal distribution. A rank sum factorial analysis is used for the data. Other dependent measures will be analyzed with parametric or non-parametric analyses, generally consisting of mixed design ANOVAs, as appropriate. Following a significant ANOVA, specific comparisons are made using Tukey's tests. Alpha is 0.05.

Power considerations: Sample sizes vary across the different studies, based on issues ranging from the study design and goals to empirical evidence for effect sizes with the proposed drug or measure. For example, "ONE-DAY" studies are designed to identify and "pilot" optimal stimulus parameters for testing specific hypotheses, and these studies may not be powered to achieve traditional levels of statistical significance. On the other hand, designing studies of drug effects on PPI and related measures in control or patient populations requires detailed power information.

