Main effects of memantine on WM will be tested by one-way ANOVA with memantine dose as a within-factor. Based on $d=0.73$ for increased WM after 20 mg MEM in controls (see above), the proposed 30 patients/dose group would yield power of 0.79 to detect significant WM-enhancing effects. While preliminary data yield less robust predictions for COMT subgroup sensitivities in memantine effects on WM performance, given the significant correlation of WM and PPI, and known impact of COMT genotype on PPI levels, we predict some differential (Val/Val > Met/Met) memantine sensitivity in this measure. If we estimate effects of COMT status on WM memantine-sensitivity to be comparable to those for PPI (65% increase in effect size), then the estimated d for Val/Val vs. Met/Met sensitivity should be 1.20, and the proposed genotype subgroup sizes would yield power of 0.65 to detect genotype-sensitive memantine effects on WM.

Secondary “biomarkers” are MMN and GBS. For MMN, positive memantine effects will be detected by increased MMN amplitude at electrode Fz. For GBS, positive memantine effects would be detected by increased 40 Hz evoked power at electrode Fz. Unlike those for PPI, predictions of positive memantine effects on MMN and GBS are not based directly on previous findings from our laboratory, using measures identical to those proposed herein. However, based on reports in healthy subjects from other laboratories of memantine effects on MMN ($d=0.87$) and ketamine effects on GBS ($d=0.69$), the proposed 30 patients/dose group would yield power of 0.90 and 0.75, respectively, to detect positive memantine effects on these measures.

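### The MCCB crossover model names no test-day or order term, so the reported negative result may be conservative for per-dose, small or single-dose effects

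*SAP*

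**What the plan says.** The SAP's MCCB paragraph lists the full set of factors: "neurocognitive domain (7 domains) was a within-subject variable along with drug (active vs. PBO), and diagnosis and dose were between-subject factors". The outcomes are T-scores for the seven domains and one comprehensive T-score. The paragraph considers altered alertness as a confounder but does not mention repeat testing. It ends with: "Analyses failed to confirm the hypothesis that MEM acutely enhanced neurocognition, in either HS or SZ patients".

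The protocol's statistics text (section 9, item j) is no fuller. In the sentence on startle data it says that "for drug studies, drug dose is used as a within-subject factor". For working memory it says: "Main effects of memantine on WM will be tested by one-way ANOVA with memantine dose as a within-factor". It adds that "the proposed 30 patients/dose group would yield power of 0.79 to detect significant WM-enhancing effects", taking d=0.73. It also states "All analyses will be conducted independently for each dose group", and keeps pooling across doses for exploratory work.

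The schedule (section 9, item g) is a two-period crossover. The treatment not given on the first day is given on the second, under the line "Test Day 2: 7-30 days after Test Day 1". No test-day, period, order or sequence term appears in either document. Section 8 of the protocol describes the ongoing healthy-subject memantine study as having a balanced order. The documents do not repeat this for the patient study and give no counts per order.

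**The concern.** When a cognitive battery is given twice, the second score can differ from the first for reasons unrelated to the drug. In a crossover, such a shift adds to the active-minus-placebo difference in subjects who took active drug second, and subtracts from it in those who took it first. With equal numbers in each order it cancels from the mean difference but stays in the spread. A model without test day treats that spread as error, so the standard error is too large and the test conservative.

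This affects the drug main effect, the comprehensive score and single-domain tests. Drug by domain is affected only by shifts that differ between domains. If orders are unequal, part of the shift also biases the drug effect.

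The SAP draws a negative conclusion, so lost power matters to its reading. A cognitive effect confined to one dose is a scenario that the trial's own results raise, because for PPI the SAP reports: "Analyses confirmed the hypothesis for the 20 mg dose of MEM in SZ patients".

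**Working it through.** **Inputs from the documents.** Alpha is 0.05 (sidedness not stated; two-sided assumed). The plan has 30 patients per dose at 10 and 20 mg, and 30 healthy subjects at 20 mg. For working memory, d=0.73 and the stated power is 0.79.

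**Assumed.** The day-2 shift p is 0.25, 0.5, 0.75 or 1.0 SD of the within-subject difference. Orders are balanced, 15/15 per group.

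**Reproducing the 0.79.** A two-sample t-test with 30 per condition at d=0.73 gives 0.794. A paired test with a difference-scale effect of 0.73 gives 0.97. The stated figure therefore matches independent groups. A paired test with n=30 reaches 0.79 at an effect of 0.523 SD of the difference. Both 0.52 and 0.73 are used below, because the protocol does not say which scale its d is on.

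**Model.** In units of the SD of the difference, D = e + p + error for active second and D = e − p + error for active first, with error N(0,1).

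- Without the term: mean of the group means, pooled within-group variance, df = Σ(n − 1). The error SD is inflated by about √(1 + p²), which is 1.03, 1.12, 1.25 and 1.41 for the four shifts.
- With the term: mean of the two order means per group, pooled within-order variance, df = Σ(n − 2).

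**Hand check, per dose, e=0.523, n=30.** Power ≈ Φ(e√n − t√(1 + p²)), with e√n = 2.86 and t = 2.045 on 29 df.

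- p=0.5: Φ(2.86 − 2.29) = 0.72
- p=1.0: Φ(2.86 − 2.89) = 0.49

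**Simulated power (100,000 replicates per cell):**

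| Test | p=0.25 | 0.5 | 0.75 | 1.0 | With term |
|---|---|---|---|---|---|
| Per dose, n=30, e=0.52 | 0.77 | 0.71 | 0.62 | 0.49 | 0.79 |
| Per dose, n=30, e=0.73 | 0.97 | 0.95 | 0.92 | 0.85 | 0.97 |
| Two patient groups, common e=0.52 | 0.98 | 0.96 | 0.93 | 0.88 | 0.98 |
| Two patient groups, common e=0.25 | 0.45 | 0.38 | 0.29 | 0.19 | 0.48 |
| Two patient groups, e=0.52 at one dose only | 0.49 | 0.42 | 0.32 | 0.21 | 0.51 |
| Two patient groups, e=0.73 at one dose only | 0.77 | 0.72 | 0.62 | 0.49 | 0.79 |
| Three groups of 30, common e=0.52 | 1.00 | 1.00 | 0.99 | 0.98 | 1.00 |

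A common effect of 0.73 in two groups keeps power of at least 0.997 throughout. For an effect at one dose only, the main effect has noncentrality (e/2)√60/s = e√15/s, where s is the error SD. Drug by dose has e/(s√(2/30)), which is also e√15/s, so its power is essentially the same.

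**Type I error, two groups.** Without the term it is about 0.04, 0.03, 0.014 and 0.006 for the four shifts; with the term it is about 0.05. For drug by domain at a 1 SD shift, it is 0.05 if the shift is common to all seven domains and 0.01–0.02 if it is confined to two.

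**Unequal orders.** Bias = p(n₁ − n₂)/(n₁ + n₂), where n₁ took active second. For illustration, 18:12 gives 0.2p. The actual counts are not given, so no bias is claimed.

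**The case against.** **Scale of the effect.** If d=0.73 is in units of the score SD, the difference-scale effect is 0.73/√(2(1 − ρ)), where ρ is the correlation between a subject's two scores. An effect of 0.52 then needs ρ of about 0.03, which is low for repeat testing. At ρ=0.5 the effect is 0.73, and a 0.5 SD shift costs only 0.97 to 0.95 per dose. This stands as a limit on the per-dose loss at the planned effect. A higher ρ also makes a given raw shift larger relative to the SD of the difference. At an assumed ρ of 0.7 and a raw shift of 0.5 SD, per-dose power at d=0.5 falls from 0.93 to 0.86. For d=0.5 at 20 mg only it falls from 0.69 to 0.54, and for a pooled d=0.2 in 60 patients from 0.50 to 0.36.

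**Pilot data.** In the balanced-order healthy-subject pilot in protocol section 8, working memory rose in seven of eight subjects and was unchanged in the eighth. That gives no sign of a shift large enough to reverse the drug effect. It is eight healthy subjects, however, and a shift need not exceed the drug effect to add error.

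**The exposed tests are weak anyway.** Even with the term, power is 0.51 for 0.52 at one dose and 0.48 for a common 0.25. Most of that shortfall is dilution and sample size, which the term cannot repair. This is true, but the omission can lower power further.

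**Unreported checks and multiplicity.** Order may have been examined without being reported; the SAP is brief, and the protocol allows mixed-design ANOVAs where suitable. Re-testing eight scores by dose after a known null result also adds multiplicity. Both are fair points. They are met by reporting whatever was done and by presenting the new results as post hoc estimates rather than further confirmatory tests.

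**Conclusion.** The concern holds. The model as written omits a standard crossover term. If scores shifted between days, the MCCB drug tests were conservative.

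At shifts of 0.5 to 1.0 SD of the difference, the loss is about 8 to 30 points for a per-dose test planned at 0.79 (0.71 to 0.49), and 9 to 30 points for an effect of 0.52 at one dose only. For a moderate effect common to both patient groups it is 2 to 10 points, and with the healthy subjects added it is 2 at most. At 0.25 SD every loss is under 3 points.

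These figures rest on an assumed shift, balanced orders, and 0.52 inferred from the protocol's own power figure. If 0.73 is the difference-scale effect, the per-dose loss is 2 points at 0.5 SD and 12 at 1.0 SD. With balanced orders there is neither bias nor a false-positive risk. The change should be made, with medium confidence in its practical size, because only the trial data can show whether a shift occurred.

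**What to change.** Add to the SAP: *As a post hoc sensitivity analysis, the MCCB domain and comprehensive T-scores were re-analysed with test day (1 or 2, within-subject) and order (placebo first or active first, between-subject) added to the model, and domain by test day in the seven-domain model.* Order as a between-subject factor with its interaction with drug gives the same adjustment.

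Report the number of subjects per order by diagnosis and dose, and the period-adjusted drug effect per dose with its 95% confidence interval. State that the unadjusted negative MCCB result may be conservative for small or dose-specific effects if scores shifted between test days. If order was already examined, say so and give the result.

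The cost is SAP wording and a re-run on data already held, since each subject's order follows from the two test days. The term uses at most one error degree of freedom per group. With no shift, power at an effect of 0.52 is unchanged to two decimals: 0.79 per dose and 0.98 pooled, with or without the term.
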